For Phase II a total sample size of 5,000 patients allows an estimation of a population attribute with a precision of less than 2.8% (i.e. width of 95% CI).

For subgroups which consist of at least 500 patients; this allows an estimation of a population attribute within the subgroup with a precision of approximately 8.9% (i.e. width of 95% CI).

For Phase III a total sample size of 10,000 patients allows an estimation of a population attribute with a precision of less than 2.0% (i.e. width of 95% CI).

Estimates for incidence rates (Phase II-III):

Estimates and confidence intervals for incidence rates (interpreted on a descriptive level) will be computed. For Phase II it is estimated to recruit approximately 2,500 patients from EU/EEA member states in the dabigatran treatment cohort whom are followed up for up to 2 years. Assuming a total treatment discontinuation and lost to follow-up rate of 25% per year a

Proprietary confidential information.

© 2014 Boehringer Ingelheim International GmbH or one or more of its affiliated companies. All rights reserved.

This document may not - in full or in part - be passed on, reproduced, published or otherwise used without prior written permission.

total of approximately 3,802 patient-years in patients from EU/EEA member states starting dabigatran will be observed.

When observing 3,802 dabigatran patient years, we will observe at least one patient with an event (ADR, MBE, stroke/SEE, etc), if the underlying incidence rate for this event is 0.079 occurrences per 100 patient years or above with a power of 95%. If we do not observe any event within the 3,802 patient years, it can be excluded with 95% confidence that the underlying true event rate is above 0.079 per 100 patient years in the population.

Based on the recent RE-LY trial (warfarin, dabigatran), it is expected that the incidence rates for stroke/SEE and MBE will be in a range of 1 to 3 per 100 patient years in the total population. The width of the two-sided 95% confidence interval of the population depends on the obtained estimate from the sample of 3,802 patient years; the following table illustrates this relationship:

Table 7.6: 2 95% Confidence intervals based on different scenarios for observed event rates (based on 3,802 patient years)

| Observed event rate per 100 patient years | Lower 95% CI for event rate per 100 patient years | Upper 95% CI for event rate per 100 patient years |
|---|---|---|
| 1 | 0.70773 | 1.372465 |

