| 2 | 1.575877 | 2.503151 |
| 3 | 2.474761 | 3.603743 |

The calculation of confidence intervals is based on the method described in Hahn, Meeker (section 7.2.2; using χ^2 -quantiles). ([R12-3048](#))

As an example, assume that the event rate for stroke per 100 patient years is 1, i.e. we observe ~38 strokes within the 3,802 patient years. The two-sided 95% confidence interval for the population incidence rate per 100 patient years is 0.71 to 1.37. Thus it can be excluded with 95% confidence that the true rate of strokes per 100 patient years is above 1.37 in the population.

For Phase III, for treatment group cohorts which initially consist of at least 2,000 patients, approximately 4,019 patient-years will be observed within the treatment regimen cohort. This approximation is based on the assumptions of a total treatment discontinuation and lost to follow-up rate of 25% per year and an individual follow-up of three years. Therefore, due to the longer individual follow-up in Phase III and thereby the longer observation time per patient, estimates of incidences based on treatment regimen cohorts which initially consist of 2,000 patients will have approximately the same precision as described above (for 2,500 patients in Phase II).

95% confidence intervals will be calculated for several outcome events. Therefore, it can be expected that false positive significant differences may arise, i.e. a treatment regimen cohort may appear by chance with a lower or a higher incidence rate for specific outcome events or for the composite endpoint variable; consequently, results have to be interpreted with care.

Proprietary confidential information.

© 2014 Boehringer Ingelheim International GmbH or one or more of its affiliated companies. All rights reserved.

This document may not - in full or in part - be passed on, reproduced, published or otherwise used without prior written permission.

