6.6 HANDLING OF MISSING DATA AND OUTLIERS

In general missing data will be handled by imputation. If cause of death is missing (neither provided on the patient vital status page nor on the outcome events page) the death will be considered as "death of unknown cause" during the data collection. If a reason of death is not

entered on the outcome CRF page but only in the free text field on the vital status page (vital status page is only to be filled for patients who discontinued the study early but allowed for vital status follow up), a medical review will be done to classify the death into vascular/non-vascular/unknown death. The classification will be documented prior to final database lock in the report planning meeting/database lock meeting minutes. For the outcome analyses regarding vascular death, as the primary approach, multiple imputation will be used to impute the unknown cause of death using the data of patients who died. The following further two alternative approaches will be considered as sensitivity analyses: (1) Unknown cause of death will be imputed as a vascular cause; (2) Unknown cause of death will be imputed as a non-vascular cause. As an additional optional sensitivity analysis for the composite outcomes, all cause death would replace vascular death ([Section 7.6](#)).

Incomplete/Missing information on outcome event occurrence / medication due to changes in visit schedule

Missed visits and visits outside visit schedule (see protocol): The CRF is set up in such a way that investigators have to enter all outcome event information and changes in medication since the last study visit; therefore complete information on outcome events is ensured even if intermittent visits are missed by using all available information from the completed study visits.

Missing outcome event date information:

The handling of missing outcome event date will be handled on a patient by patient basis. If the outcome event date for a patient is missing, all collected data for this patient will be reviewed to recover the missing outcome event date. If no information is available, the date of the outcome event will be imputed with the start of the initial treatment regimen episode+1day, if the event was documented in the first follow up visit; and with the visit date of the previous follow up visit, otherwise. The proportion of patients with partial dates will be evaluated.

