6.8 CALCULATION OF TIME TO EVENTS OR CENSORING

The derivations of time to event and time to censoring for the time to event analyses are specified in this section. The information from the outcome event pages will be used to collect events. Deaths reported via the vital status or serious adverse event page will also be included.

Events to be counted in the study period are all events with onset date \leq patient’s study termination date. Events occurring after the patient’s study termination date will NOT be included in the analysis (irrespective of whether they occur during the washout period or later) as treatment information will in general not be documented in the CRF for this time period. The event death is an exception. Death captured via the vital status page will still be considered after the patient’s discontinuation.

For composite outcome events, the onset date of the first occurring component event will be used.

The following rules will be used for the main analysis of outcome events:

The analysis will be based on the antithrombotic treatment choice selected at baseline (long-term treatment information, as collected in the following CRF question: “Please report any antithrombotic treatments that you prescribed for long term use at the time of the baseline visit, or any antithrombotic treatments that the patient was already on at the time of the baseline visit that the patient will remain on for long term use”) and the initial treatment regimen episode (as specified in [Section 6.1.2](#)). An event will be counted for the main analysis if it occurs during the initial treatment regimen episode of the antithrombotic therapy selected at baseline.

The time to event will be calculated as: event date - initial treatment regimen episode start date + 1.

The time to censoring will be calculated as initial treatment regimen episode stop date - initial treatment regimen episode start date + 1 (as described in [Table 6.1.2:1](#)).

Patients participating in a clinical trial with a drug or device or in another international drug study or registry on the use of oral anticoagulation in AF will be censored when they enter the trial/study. The exception is with clinical studies of idarucizumab (Praxbind) where explicit provision for collection of this data has now been included.

The following rules will be used for the intention-to-treat analysis of outcome events :

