The analysis will be based on the antithrombotic treatment choice selected at baseline and the study period. An event will be counted for the intention-to-treat analysis if it occurs during the study period (see exception for inclusion of death events after patient’s discontinuation, cf. [Section 6.8](#) above).

The time to event will be calculated as: event date - study period start date (=initial treatment regimen episode start date) + 1.

The time to censoring will be calculated as study period stop date - study period start date (=initial treatment regimen episode start date) + 1.

Patients participating in a clinical trial with a drug or device or in another international drug study or registry on the use of oral anticoagulation in AF will be censored when they enter the trial/study. The exception is with clinical studies of idarucizumab (Praxbind) where explicit provision for collection of this data has now been included.

For the ITT analyses, follow-up therefore begins at initial regimen episode start date and continues until occurrence of a study outcome or end of the study period, whichever occurs first (with the exception of death). Study period refers to the time from start of initial treatment regimen (see Table 6.1.2:1) to start of the post-study phase (date of study completion/discontinuation +1 day, see [Table 6.1.1:1](#) in [Section 6.1.1](#)).

Rules to be used for the analysis of adverse events (based on enrolled patients) are specified in Section 7.9.

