For the main treatment groups including the total group as defined in [Table 6.1: 1](#) and for all important outcome events including the two composite outcomes incidence rates with 95%-CIs, cumulative risks, and KM curves will be calculated on the eligible patient set on the first treatment period only. Only patients from the eligible patient set that took the prescribed treatment at least once are considered. Patients who discontinue initial antithrombotic treatment for stroke prevention permanently will be censored at date of last drug intake + 3 days (for dabigatran and non VKA treatments) and +6 days (for VKA treatment or combinations of VKA with other antithrombotic treatments) or at first intake of other relevant chronic antithrombotic treatment for stroke prevention, whatever comes first (unless the event occurred prior to the time of censoring). A patient is considered to have permanently stopped initial antithrombotic treatment for stroke prevention, if other relevant chronic antithrombotic treatment is initiated for stroke prevention or otherwise dependent on the duration of treatment interruption.

The main analysis of overall incidence rates with 95% confidence intervals, cumulative risks and KM curves will be repeated for at least the following subgroups, acknowledging the limited precision given the sample size: region (1160.129 only), chronic antiplatelet treatment (1160.136 only), antithrombotic treatment, age, gender, CHADS2, CHA2DS2-VASc and HAS-BLED risk scores. A graphical (forest-plot-like) display will additionally be prepared to

summarize the subgroup results per outcome on the eligible patient set for the first treatment period only. Additional subgroup analyses might be conducted as needed.

For all important outcome events (including composite outcomes) for patients initiating VKA at baseline, and patients initiating Dabigatran at baseline, incidence rates, cumulative risks with 95%-confidence intervals will be calculated by treatment, and for a graphical comparison Kaplan Meier curves will be plotted. These statistics will be calculated on the restricted and the matched patient sets and only the first treatment period is taken into account, i.e. patients who never took the prescribed treatment will not be included.

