For the matched and the restricted patient sets as a sensitivity analysis, the calculation of incidence rates and cumulative risks will be performed without censoring at permanent discontinuation of initial antithrombotic treatment for stroke prevention (intention to treat (ITT) approach). KM curves will be plotted.

Dependent on the number of patients receiving different antithrombotic treatment for stroke prevention and dependent on comparability of important baseline characteristics, restricted and matched patient sets may be considered for other pairwise treatment regimes. In this case, the analyses defined here for dabigatran and VKA could be performed for other treatment groups.

Further outcome events

For the further outcome events such as transient ischemic attack (TIA) or stroke (instead of TIA alone), ischemic stroke and hemorrhagic stroke incidence rates, KM estimates and KM curves will be calculated on the eligible patient sets for all main treatment groups (see [Table 6.1: 1](#)). For patients initiating VKA at baseline and patients initiating Dabigatran at baseline, above analyses will be performed on the restricted and matched patient sets on the first treatment period only.

Dependent on the number of patients receiving different antithrombotic treatment for stroke prevention and dependent on comparability of important baseline characteristics, for further outcomes mentioned above, the incidence rates, KM estimates and KM curves might be calculated on the restricted and matched patient sets for other pair-wise treatment regimes, similar to the analysis as outlined for Dabigatran and VKA.

Technical specifications

Incidence rates per 100 patient years with 95%-confidence intervals for important outcome events (single and composite outcome) will be calculated the following way. In addition these analyses will be done stratified by chronic antiplatelet treatment at baseline. Recurrent events will be disregarded for calculation of incidence rates. Incidence rate λ is defined as

$$\text{Incidence rate } \lambda \left[\frac{1}{100} \text{ pt.yrs} \right] : \\ = 100 * \frac{\text{number of patients with event}}{\frac{1}{365.25} * \sum_{\text{patients}} \text{person time at risk (event)} [\text{days}]}$$

where the denominator is the patient years under risk. The 2-sided 95% CI of λ will be calculated based on the Poisson distribution and its relation with the Chi-square distribution according to the following formula [7]:

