$$[\lambda_{\text{lower}}, \lambda_{\text{upper}}] = [\{0.5 \chi^2(\alpha/2; 2x)\}/n, \{0.5 \chi^2(1-\alpha/2; 2x+2)\}/n],$$

where $\chi^2(\gamma, r)$ is the 100 γ th percentile of a chi-square distribution with r degrees of freedom, n is the patient years under risk for the event, x is the number of patients with event, and α for (1- α) % 2-sided CIs.

Cumulative risk is defined as cumulative proportion of patients with event and will be calculated as the Kaplan-Meier estimate for failure. The Kaplan-Meier curve will be plotted. The proportion of patients with event, as well as the proportion of censored patients falling into specified intervals and the Kaplan-Meier estimate for failure will be computed for the following categories:

- ≤ 3 months
- $3 < \text{and } \leq 6$ months
- $6 < \text{and } \leq 12$ months
- $12 < \text{and } \leq 18$ months
- $18 < \text{and } \leq 24$ months
- $24 < \text{and } \leq 30$ months
- > 30 months

In the following if not stated otherwise for all analyses only patients from the restricted patient set are considered. Furthermore only the first treatment period is included (i.e. as-treated analysis) if not mentioned otherwise (like e.g. for ITT analyses).

- 1) Main analysis of composite outcome (Stroke, systemic embolism, myocardial infarction, life-threatening bleeding events and vascular death)

Acknowledging the limited precision given the sample size and the potential limitations, for the main comparison of the two treatment groups, Dabigatran and VKA, with regards to the composite outcome a multivariable Cox regression model (according to the 1160.129 and 1160.136 protocols) will be performed if those patient groups are determined to be comparable in terms of the PS analysis. The multivariable Cox regression model will include the following variables as core variables: treatment, age (<65 , $65-75$, >75), gender and the following main stroke and bleeding risk factors: prior bleed, previous stroke/TIA, previous myocardial infarction, abnormal kidney function and concomitant antiplatelets use. The following further covariates will be investigated within a model selection procedure: (sub)region, congestive heart failure, left ventricular

hypertrophy, systemic embolism, complex aortic plaque, hypertension, diabetes mellitus, PAD, CrCl, NSAID use type of AF, hepatic disease, alcohol abuse, any drug (HAS-BLED), previous OAC use (within 3 months), smoking status, and concomitant medication like antipsychotics.

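### Cumulative risk is defined as the proportion of patients with the event but estimated as 1 minus Kaplan-Meier, which modestly overstates it when other deaths are censored

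*SAP*

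**What the plan says.** The Technical specifications in SAP 7.6 give both the quantity and its estimator in one sentence: "Cumulative risk is defined as cumulative proportion of patients with event and will be calculated as the Kaplan-Meier estimate for failure". The estimate is tabulated by time category up to beyond 30 months and plotted.

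It is used widely. For dabigatran and VKA initiators, for all important outcome events and both composites, "incidence rates, cumulative risks with 95%-confidence intervals will be calculated by treatment". The main treatment groups get the same summaries, as do subgroups that include age and the stroke and bleeding risk scores. In the ITT sensitivity analysis, "the calculation of incidence rates and cumulative risks will be performed without censoring at permanent discontinuation of initial antithrombotic treatment".

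SAP 6.8 defines how follow-up ends without an event. In the main analysis, "The time to censoring will be calculated as initial treatment regimen episode stop date" minus the start date plus one day. Under ITT, "The time to censoring will be calculated as study period stop date" minus the start date plus one day. The episode stop date (SAP Table 6.1.2: 1) is, for a single-anticoagulant group, the earliest of permanent stop plus washout, start of another anticoagulant, and study completion or discontinuation.

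Protocol 7.1 says that outcome analysis will focus on incidence rates and cumulative risk, and allows Kaplan-Meier or other life-table methods.

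**The concern.** A proportion of patients with the event and a Kaplan-Meier failure estimate agree only if no patient can die without the event. Here patients can: all-cause and vascular death are themselves outcomes, and Protocol 5.1.2 classifies deaths as vascular, non-vascular or of unknown cause.

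Neither document says in words what happens to a death that is not the outcome. The rules above have no competing-event status, so such a death can only end the episode or study period and be censored. A censored patient is treated as still able to have the event later, which a dead patient is not. 1-KM then estimates risk in a population where other deaths do not occur.

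The outcomes are affected to different degrees:

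- **Stroke, TIA, systemic embolism, pulmonary embolism, MI and bleeding:** deaths without the event compete. Fatal bleeds count as life-threatening and hence major bleeding (Protocol 5.1.2), so they do not compete for bleeding.
- **Vascular death and both composites:** only non-vascular death competes.
- **All-cause death:** unaffected.

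These figures are a main descriptive product of a registry with no confirmatory testing (Protocol 7.2), and readers will take them as the share of patients affected. The excess grows with mortality, so it will be larger in any age or risk-score stratum where more patients die.

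**Working it through.** **Inputs**

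- Event rate: Protocol 7.6 says "it is expected that the incidence rates for stroke/SEE and MBE will be in a range of 1 to 3 per 100 patient years".
- Phase III follow-up and attrition: Protocol 7.6 assumes a "total treatment discontinuation and lost to follow-up rate of 25% per year and an individual follow-up of three years".
- Competing death rate: not given in the documents. I assume 1 to 5 per 100 patient-years (PY), with 8 as a stress value.

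**Reproducing the protocol's own figures.** With attrition hazard λ = −ln(0.75), patient-years are n(1 − exp(−λT))/λ.

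- n = 2,000, T = 3: 4,019.2 (protocol: 4,019).
- n = 2,500, T = 2: 3,801.9 (protocol: 3,802).

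The chi-square limits at 3,802 PY reproduce all three rows of Protocol Table 7.6: 2. The documents state no figure for cumulative risk itself.

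**Comparison at three years.** With constant event hazard s and competing death hazard d:

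- 1-KM = 1 − exp(−3s)
- cumulative incidence = s/(s + d) × (1 − exp(−3(s + d)))

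For s = 0.01 and d = 0.03, 1-KM is 1 − exp(−0.03) = 2.955%. The cumulative incidence is 0.25 × (1 − exp(−0.12)) = 2.827%. The excess is 0.128 points.

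| s per 100 PY | d per 100 PY | 1-KM (%) | Cumulative incidence (%) | Excess (points) | Relative excess |
|---|---|---|---|---|---|
| 1 | 1 | 2.955 | 2.912 | 0.044 | 1.5% |
| 1 | 3 | 2.955 | 2.827 | 0.128 | 4.5% |
| 1 | 5 | 2.955 | 2.745 | 0.210 | 7.6% |
| 3 | 1 | 8.607 | 8.481 | 0.126 | 1.5% |
| 3 | 3 | 8.607 | 8.236 | 0.370 | 4.5% |
| 3 | 5 | 8.607 | 8.001 | 0.605 | 7.6% |

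At 8 deaths per 100 PY the relative excess is about 12%.

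**Vascular death and composites.** Both rates are assumed here: outcome 1 to 5 and non-vascular death 0.5 to 2.5 per 100 PY. The excess runs from 0.022 points (2.955% against 2.934%) to 0.497 points (13.929% against 13.432%), or 0.7% to 3.8% relative.

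**Simulation.** Without discontinuation (2 million patients), s = 0.01 and d = 0.03 give an actual proportion of 2.832% against 1-KM of 2.960%; s = 0.03 and d = 0.05 give 8.005% against 8.611%. With independent discontinuation at 25% per year (400,000 patients, d = 0.03), 1-KM exceeds Aalen-Johansen by about 4.5% relative at event rates of 1, 2 and 3 per 100 PY. Treatment censoring therefore does not remove the excess.

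**Scale against sampling error.** In a 2,000-patient cohort, 1 event per 100 PY gives about 40 events in 4,019 PY. The exact Poisson interval is 0.711 to 1.355 per 100 PY, a three-year risk of 2.11% to 3.98%, far wider than the bias.

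**The case against.** The strongest reply is that the effect is small and only descriptive. That stands. Applying the protocol's attrition to all 10,000 planned EU/EEA Phase III patients gives 10,000(1 − 0.75³)/λ = 20,096 PY. Even at 5 competing deaths per 100 PY, the excess of 0.21, 0.41 and 0.61 points (1, 2 and 3 events per 100 PY) stays below the 95% half-widths of about 0.41, 0.56 and 0.66. But the bias does not shrink with sample size: at 3 events and 3 deaths per 100 PY it is 0.37 points, about one standard error (0.66/1.96 ≈ 0.34).

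A second reply is that the main analysis is as-treated, so many deaths fall after censoring and cannot compete. True, but d is the death rate while at risk, so the formula already excludes deaths after censoring or after a counted event. The real uncertainty is the value of d.

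Third, the competing-risk estimate does not restore the literal definition in the as-treated analysis. At s = 0.01 and d = 0.03 with 25% yearly attrition, only about 1.9% of patients would be observed with an on-treatment event, against 2.83% and 2.96%. This stands: most of that gap is deliberate censoring at treatment stop or switch, a separate matter.

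Fourth, the SAP names its estimator openly and could relabel the quantity as a net Kaplan-Meier risk. That would remove the contradiction but not deliver the quantity the SAP set out to report. The crude proportions also planned by interval do not deliver it either, because they ignore censoring.

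Finally, SAP 7.7 and Protocol 7.3.2 are not in the public text and may contain competing-risk work. SAP 7.6 nonetheless governs the main analyses.

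**Conclusion.** The concern holds. The estimator named in SAP 7.6 overstates the quantity it is said to measure, for every outcome except all-cause death. The direction is certain once other deaths are censored, which is inferred from the stop and censoring rules because the documents do not say it outright.

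The size rests on constant hazards and an assumed death rate. It is at most about 0.6 percentage points over three years for single outcomes up to 5 competing deaths per 100 PY, and at most about 0.5 points for vascular death and the composites over the rates assumed there. This is a descriptive-reporting error worth correcting; it does not threaten the Cox comparison of dabigatran with VKA or the incidence rates.

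**What to change.** In SAP 7.6, Technical specifications:

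- Estimate cumulative risk by the Aalen-Johansen cumulative incidence with 95% confidence intervals, at the time categories already listed, and plot those curves in place of 1-KM.
- Treat death that is not part of the outcome as a competing event; for vascular death and both composites this is non-vascular death. State that only deaths while the patient is still at risk count, since SAP 6.8 also admits vital-status deaths after study discontinuation.
- SAP 6.6 says that "multiple imputation will be used to impute the unknown cause of death using the data of patients who died" for the vascular-death analyses. Where the competing event depends on cause of death, compute the cumulative incidence in each imputed dataset and pool.
- Keep Kaplan-Meier for all-cause death, and leave incidence rates and Cox models unchanged.
- State that the as-treated version is a risk under continued initial treatment, because discontinuation and switching are still censored. Only the ITT version fully matches the stated definition.
- Name the estimator in each table, since Protocol 7.3 foresees a combined Phase II and III report.

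The cost is SAP wording and a standard SAS procedure option, using death dates and causes already collected. Protocol 7.1 appears to leave room for it. The only downside is slightly lower reported figures.
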